### 6. Study overview

In 2012 the American organization Surgeons over Seas, together with the Ministry of Health and Sanitation (MoHS) of Sierra Leone performed the Surgeons Overseas Surgical Needs Assessment (SOSAS) (7). Two years after the conduction of this study, the Sierra Leonean health care system was severely affected by the West African EVD outbreak. During and after the outbreak, several major health system interventions have taken place, such as the start of a surgical task-sharing program (11), employment of regionally hired medical doctors to support first level hospitals (12), establishment of national ambulance service and national emergency medical services, as well as mobilising of non-governmental organisations (NGOs) to support the healthcare system after the Ebola outbreak.

We will repeat the original 2012 SOSAS study to measure the effect of the 2014-2016 Ebola outbreak and subsequently also health system interventions aiming to strengthen surgical services in Sierra Leone. In this *Prevalence Study on Surgical Conditions 2019*, we will apply the same methodology as the SOSAS 2012 to measure the current surgical need. In addition to the original questionnaire we have selected five areas where we extend the survey. These five study arms were added to develop a better understanding of the needs and possibly provide support to health systems approaches that may deal with high burden of these specific surgical conditions. The six different arms of the *Prevalence Study on Surgical Conditions 2019* study are:

- 1. SOSAS Repeat
- 2. Lower Urinary Tract Symptoms (LUTS) (for male participants older than 12 y/o)
- 3. Groin Hernias
- 4. Wounds
- 5. Maternal and Perinatal Health (for female participants in their reproductive age)
- 6. Surgical Volume

#### 6.1 SOSAS Repeat

Several forthcoming publications from the SOSAS performed in Sierra Leone in 2012 revealed a large unmet need for surgical consultations. This initial Sierra Leonean study was followed by studies undertaken in multiple other countries across Africa and Asia. The awareness within public health as well as ministries about these data, have led to the aforementioned surgical resolution and investigations into the surgical system and enhancing delivery of surgical care by expanding capacity or referral systems.

In the case of Sierra Leone and the 2012 SOSAS study, the health care system has been severely affected afterward by the 2014-2016 Ebola Virus Disease (EVD) outbreak in West Africa. Up to 7% of the healthcare workers lost their lives in Sierra Leone (10), including 2 of the 10 surgeons who were employed by the MoHS. In addition to the effect on the healthcare workforce, the EVD epidemic severely impacted the provision of healthcare services and caused setbacks in the health seeking behaviour, treatment and control of surgical conditions as well as other diseases (13).

#### 6.1.1 Aim of the SOSAS repeat arm

It is the aim of the SOSAS repeat arm to establish the countrywide prevalence of surgically treatable conditions and potentially preventable deaths. Data gathered from this repeated survey will be compared against data from 2012. Both the EVD outbreak and health system-strengthening projects are expected to impact the prevalence of major surgical morbidity and mortality. One of the health strengthening projects has been the expansion of a task sharing surgical training program by the Norwegian NGO CapaCare. At the beginning of 2018, thirty-four students were partaking in the surgical training program and since the start of the programme the MoHS had posted 20 graduates in (district) hospitals (47). Since the start of the programme (47). Only 24,152 surgical procedures were identified in the country in 2012, corresponding to a

national rate of 400 surgeries per 100,000 inhabitants (4). The extent to which these barriers and enablers affect the provision of health care is part of the aim of the SOSAS repeat survey

#### 6.2. Lower urinary tract symptoms

From 2004 to 2015 the elderly population (>65 years) in Sierra Leone increased from 125,038 to 246,284, a doubling in just over a decade. This population is projected to further increase to 632,300 in 2050 (8). Lower Urinary Tract Symptoms (LUTS) are recognized as a common condition in men aged ≥40 years, and its prevalence increases with age. As the prevalence of LUTS increases with age, the burden on the healthcare system and society is also expected to increase tremendously in Sierra Leone (14).

Global estimates indicate that 2.3 billion individuals worldwide will suffer from at least one lower urinary tract symptom by 2018 (15). Although the prevalence of LUTS is estimated as being greater in women than men, still 44.7% of affected patients are men (15.) Estimates suggest that Africa will be one of the continents with the highest increase in LUTS, but direct measures of this condition from the African continent are scarce (16).

Symptoms associated with LUTS include urgency, frequency, nocturia, incomplete urination, and weak urinary stream. Causes creating LUTS in LLMIC are a broad spectrum of conditions, including benign prostatic hyperplasia, bladder stones, cancer of the bladder and prostate, detrusor muscle weakness and/or instability, diabetes, side effects of drugs, neurological conditions; for example, multiple sclerosis, spinal cord injury, cauda equina syndrome and inflammation of the prostate (prostatitis), including IgG4-related prostatitis. If left untreated, complications such as urinary retention, renal insufficiency and bladder stone can occur, requiring surgical intervention (17). LUTS is associated with high personal and societal costs, both in direct medical costs and indirect losses in daily functioning, and through its negative impact on quality of life for patients and partners (18). While nonsurgical therapy for LUTS is becoming more available globally, barriers continue to limit patient access to all therapies for LUTS in low resource environments. Illness from infectious disease, distance from clinics and lack of resources are examples of potential reasons why care seeking patterns in high resource settings may not be reflected among a rural African population (18).

#### 6.2.1. Aim of the Lower Urinary Tract Symptoms arm

The main objective is to determine the prevalence of severe LUTS among men 12 years or older in Sierra Leone. In addition, this study will also be able:

- 1. To quantify how LUTS affects Quality of Life among the study population.
- 2. To understand barriers towards health seeking behaviour for LUTS
- 3. To estimate the need for treatment of LUTS in Sierra Leone.

A potential implication of more knowledge of LUTS in Sierra Leone is the possible introduction of transurethral ethanol ablation of the prostate (TEAP). This low-cost therapy has been developed as a minimally invasive procedure for the treatment of patients with symptomatic benign prostatic hyperplasia (BPH) (45). Dehydrated ethanol is injected directly into the prostate, via the transurethral route. Dehydrated alcohol (ethanol) is inexpensive and easily accessible which makes TEAP a good alternative for treatment of severe LUTS in low-resource countries.

Depending on the outcomes of this study, it might be relevant to further investigate the feasibility of offering TEAP in Sierra Leone.

#### 6.3 Groin hernias

The surgical need of groin hernia repairs in SSA is largely unmet. Estimates demonstrate that approximately 30 inguinal hernias per 100,000 people per year are repaired in SSA (19). However, the minimum number of inguinal hernia repairs should be in the order of 200 repairs per 100,000 people per year (19). This number is more in line with figures from the United States, where 200-275 inguinal hernia repairs per 100,000 people per year are performed (20). Besides the unmet need for groin hernia repair in SSA, the (economic) burden of groin hernia is higher in SSA than in Western countries (21). In comparison with the United Kingdom, patients with groin hernias in SSA are younger of age on average, have larger hernias and there is more delay between onset of symptoms and the first presentation in a hospital (21). Appropriate management is needed to reduce the pool of groin hernias. Lowering the burden of groin hernia in SSA is desirable and can be achieved by scaling up the number of groin hernia repairs. With detailed information on the prevalence of groin hernia and the health seeking behaviour towards this condition, policy makers in SSA will be in a better position to plan the strengthening of this essential surgical service. So far, publications on the prevalence of groin hernias in SSA have major limitations, as they tend to focus on men and do physical examination is rarely performed (22-26).

#### 6.3.1 Aim of the groin hernia arm

The main aim of the groin arm is to determine the prevalence of groin hernia among children, women and men in Sierra Leone. The prevalence will be determined based on a combination of responses to the questionnaire and a physical examination. Hernia repairs are the most commonly general surgical procedure performed in Sierra Leone (4). Non-emergent surgical procedures decreased dramatically during EVD outbreak (46). This may have contributed to an increased backlog of hernia repairs performed, thus contributing to an increased prevalence compared with before the outbreak. We have chosen to include a physical examination of the groin area if household members mention to have a solid/firm and or soft/reducible mass in that area. In the SOSAS 2015 study from Nepal, a groin exam was not done, and that may be a reason for the lower-than-expected reported prevalence of inguinal hernias (27). Furthermore, we will investigate the health seeking behaviour of patients with groin hernias and estimate the recurrence rates.

#### 6.4. Wounds

Severe wounds cause considerable morbidity, mortality and an (socio) economic burden worldwide. Therefore, severe wounds are identified as one of the fifteen categories of essential surgical conditions requiring global attention (28). Although data on the prevalence of wounds in West Africa (e.g. Sierra Leone) is scarce, Wong *et al.* found that 301 of their 496 household survey respondents required some kind of surgical interventions (29). In 17% of the cases this was because of a wound (including trauma) and in 6,8% because of a burn wound. The same research group demonstrated that up to 4.8% of the 230 deceased elderly household members died as the result of a neglected wound during the past year (29). Besides the prevalence, little is known about the aetiology of the most common wounds in Sierra Leone, let alone on the spectrum of bacterial (super-) infection and resistance pattern. A previous study by Kollie et al. described 21 patients with a wound due to Mycobacterium ulcerans in neighbouring Liberia in 2012 (30). Although Buruli ulcers would need goal directed therapy with rifampicin/streptomycin and or surgical debridement and skin grafting, most ulcers are treated with over-the-counter available antibiotics. A study from Lai et al, who provided care on a ship, anchoring at six coastal West African countries, showed considerable resistance to common antibiotics (31). From clinical experiences at Masanga Hospital, a referral centre for patients with large wounds, it is known that most patients visited a traditional healer – and have started treatment (herbs and or antibiotics) – before seeking care in this rural hospital in Sierra Leone. In Sierra Leone the estimated 45.000 traditional healers (32), by far outweigh the 323 physicians in the country (33). Little is known on the type of wound treatment provided by traditional healers and the perception and health seeking behaviour of wound patients in Sierra Leone. Mallet et al described that traditional healers played a role in the West African 2014-2016 Ebola outbreak, no data was found on a potential impact the outbreak may have had on this wound treatment and health seeking behaviour (33).

#### 6.4.1. Aim of the wound arm

We believe that a large proportion of severe wounds, burns, injuries, amputations, contractures and deaths are preventable by improving knowledge on the perception and usage of modern and traditional medicine for wounds. This study aims to describe the current prevalence of wounds and the status of wound care in Sierra Leone.

The aims are:

- 1. To describe the prevalence of wounds in Sierra Leone
- 2. To study the aetiology of wounds (traumatic, infectious, snake bites, burns, vascular)
- 3. To describe the health seeking behaviour of patients with wounds
- 4. To describe the surgical need in treatment of wounds
- 5. To describe the impact of wounds on daily life
- 6. To assess the level of hypertension in Sierra Leone, together with health seeking behaviour for the hypertension.

Hypertension is an important risk factor for cardiovascular diseases (CVDs) in Africa, with rising frequency of hypertension related complications like stroke and heart failure (48,49). The rising prevalence of hypertension in SSA could lead to an upsurge in CVDs in this region if not controlled. Yet to date, detection, management and control of high blood pressure are insufficient and haphazard (50). Renewed commitment to improved surveillance and the prevention and control of hypertension of high blood pressure in Africa is critical.

#### 6.5. Maternal and Perinatal health

Sierra Leone is one of the most challenging countries to be pregnant and to give birth (35). The estimated maternal mortality of 1360 women per 100.000 live births is one of the world's highest (9). Approximately one in seventeen women die from pregnancy or childbirth-related causes, with similar high rates of neonatal mortality (36). The poor access to surgical care is regarded as one of the major causes of these poor health parameters (37,38).

This health determinant is in line with other low-income countries (LICs), where half of the pregnant and labouring women have no access to emergency obstetric surgical care (1). This means that certain emergency obstetrical situations cannot be relieved with an assisted vaginal delivery with vacuum, forceps, or a Caesarean Delivery (CD).

Countries with CD rates of less than 10% have an increased maternal and neonatal mortality (39). The 2012 SOSAS reported that only 1,9% of the total births was by CD (40). This is much lower than the threshold recommended by the WHO (38). An even lower percentage (0,4%) were delivered by assisted vaginal delivery; of all the recalled 2316 deliveries, 59% took place outside a healthcare facility (39).

To make Sierra Leone a safer place for mothers and their children, many actions have been taken. Promotion of universal access to CDs is considered as one of the key prerequisites to improve maternal and perinatal outcomes and is an integral part of WHO's comprehensive emergency obstetric care package (40).

#### 6.5.1 Aims of the maternal and perinatal health arm

This arm will provide a status update on the access and need for female and obstetrical care for women and mothers in Sierra Leone from a community perspective in the pre, during and post Ebola time frame. This study aims to describe the general status of women's health and more specific need for surgical care and family planning methods used in women in their reproductive years at the moment of the interview.

We provide a description of the amount and outcomes of pregnancies as established by this household survey of total women of reproductive age (12-50 years old) interviewed. For all deliveries we describe the actual and preferred place of delivery and means and availability of transportation (including the new ambulance transportation system) in the pre- during and post Ebola time frame. We will be able to estimate a foetal and neonatal death rate (of total births of women interviewed) and we aim to estimate a CD and assisted vaginal delivery prevalence (of total deliveries of women interviewed). Lastly the results of this study can be compared with the findings of the maternal health section of the SOSAS study in 2012. This information may help us to understand the consequences for female and maternal health during a large Ebola epidemic and it will assist us in appropriate allocation planning in the post Ebola period.

#### 6.6. Surgical volume

Before the EVD outbreak, there were ten consultant surgeons in the public government hospitals and an estimated twenty-six in private non-profit hospitals in Sierra Leone (41, 42). The LCoGS demonstrated that a surgical workforce density of less than 20 per 100,000 specialist surgeons, anaesthesiologists, and obstetricians correlates with lower rates of maternal survival (5). Based on this reported workforce density model, there should be an estimated minimum of 1,400 specialist surgeons, anaesthesiologists, and obstetricians for the 7 million inhabitants of Sierra Leone.

In 2012, a nationwide facility survey found that all surgical providers combined, performed 400 surgical procedures per 100,000 inhabitants in Sierra Leone. Private, non-profit facilities performed 54.0% of the surgical 'met need', compared with 39.6% by public and 6.4% by private

for-profit facilities. More than 90% of the estimated surgical need in Sierra Leone was unmet in 2012 (4).

Quantifying the national surgical volume by conducting a comprehensive household survey is a novel approach. Minor and major surgical procedures will be included and classified according to the essential surgical package (DCP3 volume 1) (1). These will provide an indication of the status of delivering surgical services in light of the universal health coverage. The suggested population perspective can help identifying post-operative outcomes and provide a broad overview of the contributions of the public and the private surgical providers.

#### 6.6.1. Aim of the surgical volume arm

The main aim of the study is to determine the annual volume of surgical procedures conducted in Sierra Leone from a population-based perspective. Surgical procedures will be classified using the DCP3 essential surgical package. The contributions of the public and private surgical sectors will be assessed. In addition, 7- and 30 days perioperative mortality will be measured.

### 7. Methods

#### 7.1. Study design

This is a population-based, cross-sectional household survey of surgical, urological and maternal health conditions. This study will investigate the prevalence of untreated and treated surgical conditions in Sierra Leone. Participants will be recruited nationwide. The methodology is based on a cross-sectional household survey evaluating the prevalence of surgical conditions, known as the SOSAS survey (7). In addition, five topics will be investigated more in-depth to complement the previously designed SOSAS survey.

Arms Prevalence study	Lead/Co-Lead	Target population
SOSAS Repeat	[name]	Two randomly selected household individuals
Lower Urinary Tract Symptoms	[name] [name]	All men > 12 years among the two randomly selected household individuals
Groin Hernia	[name]	Two randomly selected household individuals
Wound	[name]	Two randomly selected household individuals
Maternal and perinatal health	[name] [name]	All females >12 years <50 years among the two randomly selected household individuals
Surgical volume	[name]	All household members who have had a surgical procedure in past year

#### 7.2. Sample size and sampling

The extended SOSAS Repeat survey consists of two parts. The first part is established to identify the number of household members and to quantify the household members that have undergone a surgical procedure in the previous year. In the second part of the survey two randomly selected household members undergo a head-to-toe (verbal) examination.

The sample size for the first part of the survey is based on the surgical volume arm. For the surgical volume research arm, all household members who have undergone a surgical procedure in the previous year will be included in the study. The selection of the household members will not be done randomly in this study arm, but all the household members of the randomly selected households will take part and serve as the denominator. In the second part of the survey only two randomly selected household members will be included.

#### 7.2.1 Sample size survey first part

Based on the found surgical met need by Bolkan *et al.*, the expected period prevalence of major surgical procedures is 0.4% in Sierra Leone (4). This means that approximately 400 major surgeries per 100,000 population per year are performed in Sierra Leone. In the surgical volume arm, we estimate that at least twice as many minor procedures are performed. This results in an estimated prevalence (P) of major and minor surgical procedures combined of  $\pm$  1% per year. The level of precision is suggested within the range of 20% of the estimated prevalence, which allow us to apply an expected range (L) of (20% x 1% =) 0.002%.

#### Calculation

 $\begin{array}{l} n = Z^2 \ p \ (1 - p) \ / \ L^2 \\ n = sample size \\ Z = Confidence Interval (95% - Z is 1.96) \\ p = Estimated proportion of the prevalence of the condition looked for \\ L = Range excepted \end{array}$ 

 $n=(1.96)^2 \times 0.01 \times (1-0.01) / (0.002)^2 = 9702$ 

Under the assumption that some household representatives will not consent to partake in the survey to elucidate on the surgical conditions of the other household members, we have chosen to add a margin of 5% to the sample size. Hereby we will be able to estimate the population prevalence with a reasonable precision.

#### 7.2.2 Sample size survey second part

The sample size is based on the original SOSAS study protocol (7). A randomly selection of 1873 households will provide sufficient power to all of the six arms of the Prevalence Study on Surgical Conditions 2019. For the current power calculation we have applied the original estimated prevalence of 7.3% surgical morbidity as used by Groen et al (33). We are aware that the original SOSAS study revealed that of the 3,645 respondents, 1,352 (37%; 95% CI 34·8–39·4) people indicated that they had a wound, burn, mass, growth, deformity, or other surgical condition at the time of interview and 896 (25%; 22·9–26·2) indicated that they needed surgical care (7). This found prevalence is much higher than the prevalence used originally for the power calculation. Hereby it might seem that we are over calculating the needed power if we use the 7.3% estimated prevalence.

However, as we are repeating the SOSAS study from 2012, we have chosen to use the original prevalence of 7.3% for surgical conditions in order to be able to compare our outcomes with the original study without the need to adjust for different sample sizes afterwards. Furthermore, this current SOSAS repeat study has additional arms on LUTS, severe wounds and maternal and perinatal health. The estimated prevalence for these conditions are  $\pm$  6%,  $\pm$ 1.9% and 2%

respectively (15, 40). As we are anticipating for lower prevalence of morbidity within three of the six sub-study arms we have calculated that an overall estimated prevalence of 7.3% will provide the needed power for all the arms within this study.

The sample size calculation is based on: Kelsey 1996 'Methods in observational Epidemiology' (43). The estimated proportion of the prevalence (p) of a surgical condition is set at 7.3%. The prevalence of 7.3% is based on a pilot study of the original SOSAS research group (44). The accepted range (L) around the estimated prevalence of the disorder is set at 1%. Letter Z is Cl (95%–Z is 1.96). In the pilot study from August 2011, 95% of the targeted population was eligible, and the same proportion responded (44). This provides a response rate (95%) and eligible rate (95%) needed for the sample size correction. The sample size is further corrected for the population size and is multiplied by a design-effect (DEFF) of 1.3, assuming that surgical conditions are not very clustered. The estimated population of Sierra Leone was 7,09 million in in 2015 (8)

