#### Uflow meter

VPSS scores are evaluated in three categories, mild, moderate and severe. Only participants with a VPSS score >17, indicating a severe LUTS will be asked to complete a questionnaire related to health seeking behaviour. Also for study participants with VPSS score >17 we aim to measure flow of urine using a portable Uroflow (Uflow) meter. An Uflow meter can measure the peak urine flow rate and detect a weak urinary flow. The peak flow rate can be used as an objective measurement for detection of LUTS. The Uflow meter is a reusable plastic shaped funnel consisting of a cup and a spout divided into three chambers. The spout has a 4.6 mm diameter aperture placed at the bottom. When fluid is poured into the cup it will start to fill the funnel as well as flowing out through the aperture. At the time inflow and outflow are equal, it will maintain a constant maximal fluid level within the funnel. The accuracy and reliability of the device seems adequate for detecting LUTS or voiding dysfunction (46).

Under assumption that the prevalence of severe LUTS is 2 %, the average household size is 5,5 persons and 65 % of the population above 12 years (8,14) we estimate that from 1873 households approximately 67 participants will be asked to use the Uflow meter and complete the questionnaire about health seeking behaviour.

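### The claim that 1,873 households are enough for all six arms does not hold for LUTS, which uses about a third of the sample and misses the protocol's own ±1 point

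*Protocol*

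**What the plan says.** Section 7.2.2 on the second part of the survey makes the claim twice: "A randomly selection of 1873 households will provide sufficient power to all of the six arms", and later "we have calculated that an overall estimated prevalence of 7.3% will provide the needed power for all the arms within this study". The reason given is that LUTS, severe wounds and maternal health have lower expected prevalences (about 6%, 1.9% and 2%), so planning at 7.3% covers them.

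The inputs are one prevalence ("The estimated proportion of the prevalence (p) of a surgical condition is set at 7.3" percent), one absolute half-width ("The accepted range (L) around the estimated prevalence of the disorder is set at 1" percent) and one clustering allowance ("multiplied by a design-effect (DEFF) of 1.3, assuming that surgical conditions are not very clustered"). The result is 3,745 individuals, or 1,873 households with two selected members each.

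The table in section 7.1 gives the LUTS target population as "All men > 12 years among the two randomly selected household individuals". The maternal arm takes females above 12 and below 50 among the same two people. Section 7.2.3 on sampling individuals repeats both restrictions.

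Section 6.2.1 sets the LUTS aim: "The main objective is to determine the prevalence of severe LUTS among men 12 years or older in Sierra Leone". Section 7.3.1 plans the urine-flow measurement and the health-seeking questionnaire for severe cases only ("Under assumption that the prevalence of severe LUTS is 2" percent) and expects about 67 of them.

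**The concern.** The argument that a lower prevalence needs fewer people is correct for a fixed absolute width when everyone sampled is in the denominator. It fails when an arm keeps only about a third of the sample, and no calculation for either subset is shown.

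The outcome also shifts. LUTS is argued at 6% in the sample-size section, but its main objective is severe LUTS, put at 2% elsewhere. The count of 67 severe cases uses every household member, although only two per household are selected.

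The 7.3% argument is the only sample-size justification given for LUTS and maternal health, and section 7.3 (sample size total) caps the visits at 1,873. Arm leads would enter the field expecting a precision, and a number of severe LUTS cases, that the design does not deliver. The LUTS results are meant to estimate treatment need, and the health-seeking and urine-flow data rest on the severe cases alone.

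**Working it through.** **Inputs.** Z = 1.96, p = 7.3%, L = 1 point, DEFF = 1.3, response 0.95, eligibility 0.95, and arm prevalences 6% and 1.9% (section 7.2.2). Proportion male 0.5, proportion above 12 years 0.65, severe LUTS 2%, 5.5 members per household (section 7.3.1). Caesarean delivery 1.9% of births and 2,316 recalled deliveries in 2012 (section 6.5).

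**The plan's own figure.** 1.96² × 0.073 × 0.927 / 0.01² = 2,599.6. Then 2,599.6 × 1.3 / (0.95 × 0.95) = 3,744.6, that is 3,745 people or 1,873 households. It reproduces. Respondents after both rates: 3,745 × 0.9025 = 3,380.

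**Half-width by arm.** h = 1.96 × √(DEFF × p(1−p) / n), with n taken first at full recruitment and then after the two 95% rates.

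- LUTS denominator: 3,745 × 0.5 × 0.65 = 1,217 men; 3,380 × 0.325 = 1,098 men.
- LUTS at 6%: 1.96 × √(1.3 × 0.0564 / 1,217) = 1.52 points; with 1,098 men, 1.60 points.
- Most favourable case for LUTS (full response, DEFF 1): 1.96 × √(0.0564 / 1,217) = 1.33 points.
- Men needed for ±1 point at 6%: 3.8416 × 0.0564 / 0.0001 = 2,167 without a design effect; × 1.3 = 2,817.
- Severe LUTS at 2%: 1.96 × √(1.3 × 0.0196 / 1,217) = 0.90 point; with 1,098 men, 0.94 point. Relative to 2%: 45% and 47%.
- Wounds at 1.9%, full sample: 1.96 × √(1.3 × 0.018639 / 3,745) = 0.50 point; with 3,380, 0.52 point. Relative: 26% and 28%.
- Caesarean delivery at 1.9%, if about 2,316 deliveries are recalled again: 1.96 × √(1.3 × 0.018639 / 2,316) = 0.63 point, relative 33%. Without a design effect: 0.56 point, 29%.
- Maternal outcome at 2% counted per woman: the share of females in the age range is not given. If it is 25% to 32.5% (my assumption; 32.5% is the ceiling from the protocol's proportions), there are 845 to 1,217 women and the half-width is ±1.08 to ±0.90 points.

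**Expected severe LUTS cases.** The protocol's figure: 1,873 × 5.5 × 0.5 × 0.65 × 0.02 = 67. With the two members actually selected: 1,873 × 2 × 0.5 × 0.65 × 0.02 = 24.3, or 1,098 × 0.02 = 22.0 after the two rates.

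| Outcome | Denominator | p | Half-width (points) | Relative | Within ±1 point? |
|---|---|---|---|---|---|
| SOSAS repeat | 3,745 / 3,380 | 7.3% | 0.95 / 1.00 | 13% / 14% | yes |
| Wounds | 3,745 / 3,380 | 1.9% | 0.50 / 0.52 | 26% / 28% | yes |
| LUTS | 1,217 / 1,098 | 6% | 1.52 / 1.60 | 25% / 27% | no |
| Severe LUTS | 1,217 / 1,098 | 2% | 0.90 / 0.94 | 45% / 47% | yes |
| Caesarean delivery | 2,316 deliveries (2012 count) | 1.9% | 0.63 | 33% | yes |

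**The case against.** The only precision criterion set for the second part is ±1 point absolute, and against it most of the arms examined pass: severe LUTS, wounds and caesarean delivery all do. A reader might infer that these low-prevalence arms fail because ±1 point is half of a 2% prevalence, or because the first part of the survey works to 20% of its prevalence. The documents do not support that. The 20% is set for surgical volume only, and wounds and caesarean delivery achieve about half of the ±1 point, not the whole of it. A reader might also infer that most arms are cut down to subsets. Only LUTS and maternal health are: SOSAS, hernia and wounds use everyone selected, and surgical volume uses all household members with its own calculation.

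The LUTS figures may also be somewhat pessimistic. DEFF 1.3 goes with about 50 respondents per cluster (3,745 / 75), whereas men above 12 number about 15 (1,098 / 75). If the implied intracluster correlation is held constant (an assumption), ρ = 0.3 / 49 ≈ 0.006 and DEFF ≈ 1 + 14 × 0.006 ≈ 1.08. The half-widths become about ±1.46 points at 6% and ±0.86 at 2%. Replacing refusing or empty households should also recover part of the two 5% losses.

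Finally, 6% is not plainly the wrong outcome, because the executive summary describes the arm's purpose as the prevalence of LUTS, without the word severe.

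All of this stands, but it does not rescue the claim. LUTS at 6% misses ±1 point even with full response and no design effect (±1.33).

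**Conclusion.** The statement that 1,873 households suffice for all six arms is not true as written. It fails on the protocol's own prevalence, proportions and target: LUTS at 6% gets ±1.5 to ±1.6 points where ±1 was set. Power here means precision of an estimate; no hypothesis test is involved.

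For severe LUTS, the stated main objective, ±1 point is met at about ±0.9. The estimate would still carry a relative half-width of 45-47% and rest on about 22-24 men, roughly a third of the 67 expected. For wounds and caesarean delivery the absolute criterion is met with relative precision of about 26-33%. Since no relative target exists for the second part, that is something to disclose, not a failure.

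The LUTS result needs no outside assumption. The caesarean figure assumes the 2012 number of deliveries and ignores clustering within women. A per-woman maternal figure depends on the assumed age share and lies close to ±1 point on either side. The 3,745 itself, the SOSAS estimate and the sampling scheme are unaffected, and the documents do not show that a larger survey is required.

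**What to change.** In section 7.2.2 (second part), delete the two sentences that extend the sample size to all arms. Replace them with a short table giving, for each arm:

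- the expected denominator (men above 12 for LUTS; women above 12 and below 50, or deliveries, for maternal health; all selected people for SOSAS, hernia and wounds; all household members for surgical volume);
- the assumed prevalence of that arm's main outcome, where the protocol gives one;
- the 95% half-width, absolute and relative, with the design effect used.

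State whether LUTS at 6% or severe LUTS at 2% is the planned main outcome, and make the executive summary, section 6.2.1 and section 7.2.2 agree. In section 7.3.1, replace 5.5 members by the two selected, so that 67 becomes about 24, and read the urine-flow and health-seeking plans against that number.

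The cost is protocol wording and one table. No extra participants or field time are needed. The price is a less favourable stated precision for LUTS.
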